To evaluate the elimination of neutrophils from the mucosa by histopathology at Week 52.	Absence of lamina propria and epithelial neutrophils at Week 52 assessed by 
 GHAS RHI
Exploratory (not in protocol)	
To evaluate the efficacy of treatment with LY3074828 as superior to placebo in PRO response (defined as 30% reduction from baseline in AP or SF with neither worse than baseline) at Week 12	Proportion of subjects achieving PRO response at Week 12.
To evaluate the efficacy of treatment with LY3074828 as superior to placebo in PRO response (defined as 30% reduction from baseline in AP or SF with neither worse than baseline) at Week 52	Proportion of subjects achieving PRO response at Week 52.
To evaluate the effect of LY3074828 on durability of PRO response at Week 52	Proportion of subjects achieving PRO response at Week 52 who also had PRO response at Week 12.
To evaluate the effect of LY3074828 on durability of PRO remission at Week 52	Proportion of subjects achieving PRO remission at Week 52 who also had PRO remission at Week 12.
To evaluate the effect of LY3074828 on PRO remission at Week 52 among PRO responders at Week 12	Proportion of subjects achieving PRO remission at Week 52 out of those patients who had PRO response at Week 12.
To evaluate the efficacy of treatment with LY3074828 as superior to placebo in the composite of endoscopic response and PRO remission at Week 12	Proportion of subjects achieving both endoscopic response and PRO remission at Week 12
To evaluate the effect of LY3074828 on the proportion of subjects with the composite of endoscopic response and PRO remission at Week 52	Proportion of subjects achieving both endoscopic and PRO remission at Week 52

Objectives and Endpoints

Objectives	Endpoints
To evaluate the effect of LY3074828 on durability of the composite endoscopic response and PRO remission at Week 52	Proportion of subjects achieving both endoscopic response and PRO remission at Week 52 out of the patients with endoscopic response and PRO remission at Week 12
To evaluate the efficacy of treatment with LY3074828 as superior to placebo in PRO1 remission (defined as SF \leq 1.5 and AP \leq 1 and no worse than baseline) at Week 12	Proportion of subjects achieving PRO1 remission at Week 12.
To evaluate the effect of LY3074828 on the proportion of subjects with PRO1 remission at Week 52	Proportion of subjects achieving PRO1 remission at Week 52.

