Measure	Description / Timing	Variable	Derivation / Comment
CDAI	
The CDAI is an 8-item disease activity measure comprised of 3 patient-reported and 5 physician-reported/laboratory items. Subject responses are summed over a 7-day period and subsequently weighted, yielding a total score range of 0-600 points. For all endpoints derived using CDAI in this table, 7 days of subject-reported data within a 12-day period prior to a visit will be utilized to calculate scores. Data will be excluded from score calculations when collected on day(s) of colonoscopy prep, day of colonoscopy procedure, and 2 days after colonoscopy procedure.
 
If after excluding these values 4 days of data are not available, the value will be set to missing. CDAI data is collected at every visit during the Screening through Follow-Up Periods visits.
	PRO Remission	
PRO remission is defined as SF \leq2.5 and AP \leq1 and no worse than baseline at Week x.
 
PRO remission = (7 day average of SF) \leq2.5 and no worse than baseline and (7 day average of AP score) \leq1 and no worse than baseline
 
SF captures the number of liquid or very soft stools.
 
AP score is classified as 0=none, 1=mild, 2=moderate, 3=severe.
 
Endpoints:
 
 • Proportion of subjects with PRO remission at Week 12 • Proportion of subjects with PRO remission at Week 52
		PRO Response	
PRO response is defined as a decrease of at least 30% in either SF or AP and neither of them worse than baseline
 
Endpoints:
 
 • Proportion of subjects with PRO response at Week 12 • Proportion of subjects with PRO response at Week 52
		Durability of PRO Remission	
 • Endpoint: Proportion of subjects with PRO remission at both Weeks 12 and 52 (ie, of those subjects who achieved a PRO remission at Week 12, the proportion who maintained a PRO remission at Week 52).
		Durability of PRO Response	
 • Endpoint: Proportion of subjects with PRO response at both Weeks 12 and 52 (ie, of those subjects who achieved a PRO response at Week 12, the proportion who maintained a PRO response at Week 52).

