		PRO Remission in PRO Responders	
Endpoint: Proportion of subjects with PRO remission at Week 52 and PRO response at Week 12 (ie, of those subjects who achieved a PRO response at Week 12, the proportion who achieved a PRO remission at Week 52).

Description and Derivation of Efficacy Endpoints

Measure	Description / Timing	Variable	Derivation / Comment
		PRO2 Response	PRO2 is a 2-item index comprised of the SF and AP items from the CDAI (weighted). The total PRO2 is comprised of the average daily scores over 7 days, weighted using the CDAI multiplication factors for SF and AP items. (See Appendix 6 for complete details on the CDAI form.) PRO2 = (7 day average of SF)*2 + (7 day average of AP score)*5 Proportion of subjects with PRO2 reduction of at least 5 points at Week x compared with baseline. Endpoints: 
 • Proportion of subjects with PRO2 response at Week 12 • Proportion of subjects with PRO2 response at Week 52
		PRO2 Remission	See PRO2 calculations above. Proportion of subjects with PRO2 <8 at Week x . Endpoints: 
 • Proportion of subjects with PRO2 remission at Week 12 • Proportion of subjects with PRO2 remission at Week 52
		Durability of PRO2 Response	Endpoint: Proportion of subjects with PRO2 response at both Weeks 12 and 52 (ie, of those subjects who achieved a PRO2 response at Week 12, the proportion who maintained a PRO2 response at Week 52).
		Durability of PRO2 Remission	Endpoint: Proportion of subjects with PRO2 remission at both Weeks 12 and 52 (ie, of those subjects who achieved a PRO2 remission at Week 12, the proportion who maintained a PRO2 remission at Week 52).
		PRO1 Remission	PRO1 remission is defined as SF ≤ 1.5 and AP ≤ 1 and no worse than baseline for both SF and AP at Week x . PRO remission = (7 day average of SF) ≤ 2.5 and no worse than baseline and (7 day average of AP score) ≤ 1 and no worse than baseline. Endpoints: 
 • Proportion of subjects with PRO1 remission at Week 12 • Proportion of subjects with PRO1 remission at Week 52

Description and Derivation of Efficacy Endpoints

Measure	Description / Timing	Variable	Derivation / Comment
		CDAI Total Score	The derivation is based on the CDAI questionnaire in Appendix 6 . It also utilizes the standard weights table in that section. Endpoint : Changes from baseline.

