		CDAI Remission	See CDAI Total Score calculations above. Proportion of subjects with CDAI Total Score <150 at Week x. Endpoints: 
 • Proportion of subjects with CDAI remission at Week 12 • Proportion of subjects with CDAI remission at Week 52
		CDAI Response	See CDAI Total Score calculations above. Proportion of subjects achieving a CDAI reduction of ≥ 100 from baseline or CDAI <150 at Week x. Endpoints: 
 • Proportion of subjects with CDAI response at Week 12 • Proportion of subjects with CDAI response at Week 52
		CDAI Remission in CDAI Responders	Endpoints: 
 • Among CDAI responders at Week 12, the proportion of subjects with CDAI remission at Week 52.
Composite Endoscopic and PRO Remissions	Endoscopic remission: See SES-CD section above. PRO remission: See CDAI section above.	Composite of Endoscopic and PRO Remissions	Proportion of subjects achieving both endoscopic and PRO remissions at Week x. Endpoints : 
 • Proportion of subjects achieving both endoscopic and PRO remissions at Week 12 • Proportion of subjects achieving both endoscopic and PRO remissions at Week 52
		Durability of Composite Endoscopic and PRO Remissions	Endpoint : Proportion of subjects achieving both endoscopic and PRO remissions at Week 52 who also had both endoscopic and PRO remissions at Week 12 (that is, of those subjects who achieved both endoscopic and PRO remissions at Week 12, the proportion who maintained both endoscopic and PRO remissions at Week 52).

Description and Derivation of Efficacy Endpoints

Measure	Description / Timing	Variable	Derivation / Comment
Composite Endoscopic Response and PRO Remission	Endoscopic response: See SES-CD section above. PRO remission: See CDAI section above.	Composite of Endoscopic Response and PRO Remission	Proportion of subjects achieving both endoscopic response and PRO remission at Week x. Endpoints: 
 • Proportion of subjects achieving both endoscopic response and PRO remission at Week 12 • Proportion of subjects achieving both endoscopic and PRO remissions at Week 52

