		Durability of Composite Endoscopic Response and PRO Remission	Endpoint: Proportion of subjects achieving both endoscopic response and PRO remission at Week 52 who also had both endoscopic response and PRO remission at Week 12 (that is, of those subjects who achieved both endoscopic response and PRO remission at Week 12, the proportion who maintained both endoscopic response and PRO remission at Week 52).

Abbreviations: AP = abdominal pain; CD = Crohn’s disease; CDAI = Crohn’s Disease Activity Index; PRO = patient-reported outcomes; SES-CD = Simple Endoscopic Score for Crohn’s Disease; SF = stool frequency.

Table AMAG.6.8 describes the analysis methods, population, and time points/associated study periods for each analysis.

Table AMAG.6.8. Description of Efficacy Analyses

Measure	Variable	Analysis Method (Section 6.1.6)	Population (Table AMAG.6.1)	Time Point
SES-CD	Endoscopic Response	Primary Analysis: Logistic regression analysis with NRI	ITT Population	Week 12
		Secondary Analysis: CMH with NRI	ITT Population	Week 12
		Descriptive Statistics with NRI	EHO Group 2	All scheduled visits through Week 52
	Endoscopic Remission	Primary Analysis: Logistic regression analysis with NRI	ITT Population	Week 12
		Secondary Analysis: CMH with NRI	ITT Population	Week 12
		Descriptive Statistics with NRI	EHO Group 2	All scheduled visits through Week 52
	Durability of Endoscopic Response	Descriptive Statistics with NRI	EHO Group 2	Week 52
Durability of Endoscopic Remission	Descriptive Statistics with NRI	EHO Group 2	Week 52	
CDAI	PRO Remission	Primary Analysis: Logistic regression analysis with NRI	ITT Population	Week 12
		Secondary Analysis: CMH with NRI	ITT Population	Week 12
		Descriptive Statistics with NRI	EHO Group 2, EHO Group 3	All scheduled visits through Week 120 (where applicable)
	PRO Response	Primary Analysis: Logistic regression analysis with NRI	ITT Population	Week 12
		Secondary Analysis: CMH with NRI	ITT Population	Week 12
		Descriptive Statistics with NRI	EHO Group 2, EHO Group 3	All scheduled visits through Week 120 (where applicable)
	Durability of PRO Remission	Descriptive Statistics with NRI	EHO Group 2	Week 52
	Durability of PRO Response	Descriptive Statistics with NRI	EHO Group 2	Week 52
	PRO Remission in PRO Responders	Descriptive Statistics with NRI	EHO Group 2	Week 52
	PRO2 Response	Primary Analysis: Logistic regression analysis with NRI	ITT Population	Week 12

Description of Efficacy Analyses

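### SAP Table AMAG.6.7 contradicts itself on two exploratory endpoints, PRO1 remission and the Week 52 composite of endoscopic response with PRO remission; in each case the stray text duplicates another endpoint

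*SAP*

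**What the plan says.** **PRO1 remission.** The derivation cell in SAP Table AMAG.6.7 opens with "PRO1 remission is defined as SF ≤ 1.5 and AP ≤ 1 and no worse than baseline for both SF and AP". The Week 12 objective in Table AMAG.4.1 gives the same limits. The cell then states its formula: "PRO remission = (7 day average of SF) ≤ 2.5 and no worse than baseline", followed by a mean abdominal pain (AP) score of at most 1, also no worse than baseline. The PRO remission row earlier in the same table carries that same formula.

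**Response composite.** The Table AMAG.4.1 objective is "To evaluate the effect of LY3074828 on the proportion of subjects with the composite of endoscopic response and PRO remission at Week 52", but the endpoint printed beside it combines endoscopic remission with PRO remission. In Table AMAG.6.7 the variable name, the general rule for any week and the Week 12 bullet all use endoscopic response. The Week 52 bullet is "Proportion of subjects achieving both endoscopic and PRO remissions at Week 52", identical to the Week 52 bullet of the remission composite. The durability row returns to response: "the proportion who maintained both endoscopic response and PRO remission at Week 52". Note e of Table AMAG.6.6 also names response, for Weeks 12 and 52.

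**Status.** Table AMAG.4.1 lists all of these as exploratory and not in the protocol. Table AMAG.6.8 plans logistic regression and a CMH test for PRO1 at Week 12 in the ITT population, with descriptive summaries in EHO Groups 2 and 3 through Week 120. The Week 52 composite is descriptive only, in EHO Group 2.

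**The concern.** A formula and an endpoint bullet are the lines a programmer is likely to work from, and here they disagree with the definitions next to them. The protocol cannot settle the matter, because these endpoints exist only in the SAP.

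For PRO1, the planned Week 12 comparison with placebo would repeat the PRO remission comparison, and the tighter SF limit would never be examined. For the composite, Week 52 would follow one rule while Week 12 and durability follow another. The endpoint entries in the two tables also agree with each other, so checking one against the other would appear to confirm the wrong version. If the conflict is noticed only after unblinding, the choice of definition is no longer pre-specified.

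**Working it through.** **Figures at stake.** The plan states no rate for either endpoint, so there is no figure to reproduce on this point. The one design figure is the 81% power in protocol section 10.1 (60 per arm, 35% against 15%, two-sided 0.10). With pooled rate 0.25:
- null SE = √(2 × 0.25 × 0.75 / 60) = 0.0791
- alternative SE = √((0.35 × 0.65 + 0.15 × 0.85) / 60) = 0.0769
- z = (0.20 − 1.645 × 0.0791) / 0.0769 = 0.91, giving power of about 0.818

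This agrees with the stated 81% and uses neither endpoint.

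**PRO1: where the two rules differ.** Both require mean AP ≤1 and neither item worse than baseline. They differ only when 1.5 < mean SF ≤ 2.5.
- With 7 diary days, this is an SF total of 11 to 17 (11/7 = 1.57; 17/7 = 2.43).
- With 4 days, the minimum for a non-missing score, it is a total of 7 to 10 (7/4 = 1.75; 10/4 = 2.50).

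Subjects in that band who also meet the AP and baseline conditions are PRO1 remitters by the formula but not by the definition. No subject moves the other way, because SF ≤1.5 implies SF ≤2.5. The formula therefore overstates PRO1 remission or leaves it equal, and gives exactly the PRO remission rate.

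**Composite: direction of the error.** Inputs are entry SES-CD ≥7 (ileal-colonic) or ≥4 (isolated ileal) from protocol section 6.1, and from Table AMAG.6.7 response as a 50% reduction and remission as SES-CD <4 or <2 with no subscore above 1.
- Ileal-colonic: the smallest fall that ends in remission is 7 to 3, (7 − 3)/7 = 57%.
- Isolated ileal: the smallest is 4 to 1, (4 − 1)/4 = 75%.

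Both exceed 50%, so every eligible remitter is also a responder. Putting remission in place of response can only lower the Week 52 count or leave it equal.

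**Composite: conflict with durability.** Take an ileal-colonic subject with SES-CD 20 at baseline and 8 at Weeks 12 and 52, in PRO remission at both visits. The fall is (20 − 8)/20 = 60%, a response, but 8 is not below 4.
- Week 12 response composite: success.
- Durability of the response composite: success.
- Week 52 endpoint as worded: failure.

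Durability successes should be a subset of Week 52 successes. Under the printed wording they need not be, and the durability numerator can exceed the Week 52 numerator.

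**The case against.** The best defence is that the SAP also states the right rule in each place. The PRO1 cell begins with SF ≤1.5, and the stray formula is labelled PRO remission, not PRO1 remission. For the composite, the objective, the variable name, the general rule, Table AMAG.6.6 and the durability row all say response. Nothing in the SAP says that the formula or the bullet governs. This stands: the fault is a contradiction that could produce a wrong number, and a reader who inferred that it must do so would go too far.

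Two other strong readings are tempting and also fail.
- A reader might infer that every subject with mean SF above 1.5 and up to 2.5 and AP ≤1 is miscounted. The formula also requires no worsening from baseline, and entry is allowed on pain alone. A subject with SF 1.0 at baseline and 2.0 at Week 12 fails both rules. Non-responder imputation also makes subjects who stop treatment before the visit non-responders.
- A reader might infer that any change in the composite from Week 12 to Week 52 would be purely a change of definition. Under the printed wording it would mix definition, disease course and the Period 2 change of treatment. The formal Week 12 result is also in the ITT population, whereas Week 52 is in EHO Group 2.

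It is also fair that no statistical method is in dispute, and that the response composite can be recovered because its components are collected and defined separately. That limits the importance, but it does not remove the conflict.

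**Conclusion.** The text is wrong as written, with low severity. Three objectives in Table AMAG.4.1 are exposed: PRO1 remission at Week 12, PRO1 remission at Week 52, and the response composite at Week 52. The Week 12 response composite and its durability endpoint are correctly worded. Of the three exposed, only PRO1 at Week 12 has a planned test.

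The direction is known if the stray text is followed: PRO1 overstated or equal, the Week 52 composite understated or equal. The second direction assumes that subjects meet the SES-CD entry limits. The size cannot be computed from the documents. PRO remission itself, a secondary endpoint, is defined in its own row and is not affected. Nor are the primary endpoint, the other secondary endpoints or the sample size.

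**What to change.** - **Table AMAG.6.7, PRO1 remission:** relabel the formula as PRO1 remission and set it to a 7-day average SF ≤1.5 and a 7-day average AP score ≤1, each no worse than baseline.
- **Table AMAG.6.7, response composite, Week 52 bullet:** name endoscopic response together with PRO remission.
- **Table AMAG.4.1, endpoint beside the Week 52 response-composite objective:** make the same change.

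These edits restore the SAP's own definitions. The cost is three lines of text, with no effect on data collection or patients. If programming has started, confirm which rule was coded for each endpoint. Corrected outputs need only data already collected.

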6.11. Health Outcomes/Quality-of-Life Analyses

There are 9 self-administered questionnaires used for measuring health outcomes in this trial. CDAI is not included in Table AMAG.6.9, as it is described in the previous section. The health outcomes derivations/analyses are described in Table AMAG.6.10 and Table AMAG.6.11.

Table AMAG.6.9. Health Outcomes Endpoints

Health Outcomes Endpoint	Response
PGRS (Patient’s Global Rating of Severity) (Daily) ^a PGRC (Patient’s Global Rating of Change) ^a IBDQ (Inflammatory Bowel Disease Questionnaire score) ^a FACIT-Fatigue (Functional Assessment of Chronic Illness Therapy–Fatigue) ^a SF-36 (Medical Outcomes 36-Item Short Form Health Survey score) Version 2 ^a [REDACTED]	Weeks 12, 52
BMC (Bowel Movement Count) (Daily) ^b QIDS-SR16 (Quick Inventory of Depressive Symptomatology–Self Report [16 Items]) ^b [REDACTED]	Week 12

^a Secondary Endpoints

^b Exploratory Endpoints

Table AMAG.6.10. Description and Derivation of Health Outcomes Endpoints Except CDAI

[figure not shown]
Measure	Description / Timing	Variable	Derivation / Comment
PGRS	
The PGRS is a 1-item patient-rated questionnaire designed to assess the subjects' rating of their disease symptom severity over the past 24 hours. Responses are graded on a 6-point scale in which a score of 1 indicates the subject has no symptoms (that is, "none") and a score of 6 indicates that the subject's symptom are "very severe."
 
PGRS is collected daily during Screening, Periods 1, 2, and 3, but only the last 12 days prior to each visit in the Schedule of Activities of the protocol will be considered for analysis.
	Mean PGRS score	
7 days of subject-reported data within a 12-day period prior to a visit will be utilized to calculate the average PGRS scores. Data will be excluded from score calculation when collected on day(s) of colonoscopy prep, day of colonoscopy procedure, and two days after colonoscopy procedure.
 
If after excluding these values 4 days of data are not available, the value will be set to missing.

PGRC	
The PGRC scale is a patient-rated instrument designed to assess the subjects' rating of change in their symptom(s). Responses are graded on a 7-point Likert scale in which a score of 1 indicates that the subject's symptom is "very much better," a score of 4 indicates that the subject's symptom has experienced "no change," and a score of 7 indicates that the subject's symptom is "very much worse."
 
PGRC is assessed at Weeks 4, 11-12, 16, 24, 32, 44, 52, 56, 72, 88, and 104 during Periods 1, 2, and 3 per the Schedule of Activities in the protocol.
	PGRC score	PGRC is a single score collected at each study visit. No derivation is required for analysis.
IBDQ	
The IBDQ is a 32-item self-administered questionnaire. The IBDQ has 4 dimensions: bowel symptoms (10 items), systemic symptoms (5 items), emotional function (12 items), and social function (5 items) (Feagan et al. 2011). Responses are graded on a 7-point Likert scale in which 7 denotes "not a problem at all" and 1 denotes "a very severe problem." Scores range from 32 to 224; a higher score indicates a better quality of life.
 
IBDQ is assessed at Screening, Baseline, and Weeks 4, 11-12, 16, 24, 32, 44, 52, 56, 72, 88, and 104 during Periods 1, 2, and 3 per the Schedule of Activities in the protocol.
	IBDQ score	The scores from each of the 32 questions will be summed to find the total IBDQ score. Instructions for handling missing values are described in Appendix 3 .
		IBDQ Responder	Proportion of subjects achieving the IBDQ MCID where MCID is defined as an improvement (increase from baseline) ≥ 16 points in the IBDQ score.

Description and Derivation of Health Outcomes Endpoints Except CDAI

Measure	Description / Timing	Variable	Derivation / Comment
FACIT-Fatigue	
The FACIT-Fatigue is a 13-item instrument developed to measure fatigue in chronic illness subjects. It has been validated for use in IBD subjects. Total score ranges from 0 to 52 based on a rating of 4-point Likert scale. Higher scores are better.
 
FACIT-Fatigue is assessed at Screening, Baseline, and Weeks 4, 11-12, 16, 24, 32, 44, 52, 56, 72, 88, 104, and 120 during Periods 1, 2, 3, and Follow-Up per the Schedule of Activities in the protocol.
	FACIT-Fatigue total score	
The algorithm for scoring the FACIT-Fatigue is found in Appendix 4, following the questionnaire. All responses are added with equal weight to obtain the total score. In cases where some answers may be missing, a total score is prorated from the score of the answered items, so long as more than 50% of the items (ie, at least 7 of 13) were answered.

		FACIT-Fatigue Responder	
Proportion of subjects achieving the FACIT-Fatigue MCID where MCID is defined as an improvement (increase from baseline) ≥ 3.56 points in the FACIT-Fatigue score.

Description and Derivation of Health Outcomes Endpoints Except CDAI

Measure	Description / Timing	Variable	Derivation / Comment
SF-36 Version 2	
The SF-36 Version 2 is a 36-item patient-administered measure designed to be a short, multi-purpose assessment of health in the areas of physical functioning, role-physical, role-emotional, bodily pain, vitality, social functioning, mental health, and general health. The 2 over-arching domains of mental well-being and physical well-being are captured by the MCS and PCS scores. The summary scores range from 0 to 100, with higher scores indicating better levels of function and/or better health. Items are answered on Likert scales of varying lengths.
 
SF-36 is assessed at Screening, Baseline, and Weeks 4, 11-12, 16, 24, 32, 44, 52, 56, 72, 88, 104, and 120 during Periods 1, 2, 3, and Follow-Up per the Schedule of Activities in the protocol.
	
SF-36 Domain Scores:
 
 • physical functioning • role-physical • role-emotional • bodily pain • vitality • social functioning • mental health • general health 
SF-36 PCS SF-36 MCS
	
Health Outcomes Scoring Software 5.0 will be used to calculate the scores.

		
SF-36 PCS Responder SF-36 MCS Responder
	
Proportion of subjects achieving the SF-36 PCS MCID where MCID is defined as an improvement (increase from baseline) ≥ 2.5 points in PCS.
 
Proportion of subjects achieving the SF-36 MCS MCID where MCID is defined as an improvement (increase from baseline) ≥ 2.5 points in MCS.

Description and Derivation of Health Outcomes Endpoints Except CDAI

Measure	Description / Timing	Variable	Derivation / Comment
BMC	
Due to the significant impact of SF on subjects’ lives, the BMC will be used to measure “stool frequency in the past 24 hours” using an electronic daily diary. In order to encourage consistent diary recording, subjects should enter daily diary data continuously throughout the study.
 
BMC is collected daily during Screening, Periods 1, 2, 3, and Follow-Up, but only the last 12 days prior to each visit in the Schedule of Activities of the protocol will be considered for analysis.
	Mean BMC score	
7 days of subject-reported data within a 12-day period prior to a visit will be utilized to calculate the average BMC scores. Data will be excluded from score calculation when collected on day(s) of colonoscopy prep, day of colonoscopy procedure, and two days after colonoscopy procedure.
 
If after excluding these values 4 days of data are not available, the value will be set to missing.

QIDS-SR16	
The QIDS-SR16 is a self-administered 16-item instrument intended to assess the existence and severity of symptoms of depression as listed in the American Psychiatric Association’s Diagnostic and Statistical Manual of Mental Disorders, 4th Edition (DSM-IV) (APA 1994). A patient is asked to consider each statement as it relates to the way they have felt for the past 7 days. There is a 4-point scale for each item ranging from 0 to 3. The 16 items corresponding to 9 depression domains are summed to give a single score ranging from 0 to 27, with higher scores denoting greater symptom severity. The domains assessed by the instrument include: 1) sad mood, 2) concentration, 3) self-criticism, 4) suicidal ideation, 5) interest, 6) energy/fatigue, 7) sleep disturbance (initial, middle, and late insomnia or hypersomnia), 8) decrease/increase in appetite/weight, and 9) psychomotor agitation/retardation. Additional information and the QIDS-SR16 questions may be found at the University of Pittsburgh IDS/QIDS internet page [www.http://www.ids-qids.org/].
 
QIDS-SR16 is assessed Weeks -4, 0, 11-12, 52, 104, and 120 during Screening, Periods 1, 2, 3, and Follow-Up.
	QIDS-SR16 total score	The algorithm for scoring the QIDS-SR16 is found in Appendix 5 .

Description and Derivation of Health Outcomes Endpoints Except CDAI

Measure	Description / Timing	Variable	Derivation / Comment
CCI			

CCI Therapy-Fatigue; IBD = inflammatory bowel disease; IBDQ = Inflammatory Bowel Disease Questionnaire; MCS = mental component summary; CCI
CCI PCS = physical component summary; PGRC = Patient's Global Rating of Change; PGRS = Patient's Global Rating of Severity; QIDS-SR16 = Quick Inventory of Depressive Symptomatology-Self Report (16 Items); SF-36 = 36-Item Short Form Health Survey.

Table AMAG.6.11. Description of Health Outcomes Analyses

Measure	Variable	Analysis Method (Section 6.1.6)	Population (Table AMAG.6.1)	
PGRS	Mean PGRS score	Primary Analysis: MMRM – change from baseline	ITT Population	
		Sensitivity Analysis: ANCOVA (mBOCF) – change from baseline	ITT Population	
		Descriptive statistics – observed values	EHO Group 2	
PGRC	PGRC score	Descriptive statistics – observed values	ITT Population, EHO Group 2	
IBDQ	IBDQ score	Primary Analysis: MMRM – change from baseline	ITT Population	
		Sensitivity Analysis: ANCOVA (mBOCF) – change from baseline	ITT Population	
		Descriptive statistics – observed values	EHO Group 2	
	IBDQ Responder	Primary Analysis: Logistic regression analysis with NRI	ITT Population	
		Descriptive statistics with NRI	EHO Group 2	
FACIT- Fatigue	FACIT-Fatigue Total score	MMRM – change from baseline	ITT Population	
		Descriptive statistics – observed values	EHO Group 2	
	FACIT-Fatigue Responder	Primary Analysis: Logistic regression analysis with NRI	ITT Population	
		Descriptive statistics with NRI	EHO Group 2	
SF-36 Version 2	SF-36 Domain Scores: 
 • physical functioning • role-physical • role-emotional • bodily pain • vitality • social functioning • mental health • general health SF-36 physical component score SF-36 mental component score	MMRM – change from baseline	ITT Population	
		Descriptive statistics – observed values	EHO Group 2	

[figure not shown]
Measure	Variable	Analysis Method (Section 6.1.6)	Population (Table AMAG.6.1)	
	SF-36 PCS Responder SF-36 MCS Responder	Primary Analysis: Logistic regression analysis with NRI	ITT Population	
		Descriptive statistics with NRI	EHO Group 2	

BMC	Mean BMC score	Primary Analysis: MMRM – change from baseline	ITT Population	
		Sensitivity Analysis: ANCOVA (mBOCF) – change from baseline	ITT Population	
		Descriptive statistics – observed values	EHO Group 2	
		Additional exploratory/psychometric analyses will be described in a separate health outcomes SAP; these analyses will be conducted by Lilly GPORWE.		
QIDS-SR16	QIDS-SR16 total score	MMRM – change from baseline	ITT Population	
		Descriptive statistics – observed values	EHO Group 2	

Abbreviations: ANCOVA = analysis of covariance; BMC = bowel movement count; CCI [redacted]; EHO = efficacy and health outcomes; FACIT-Fatigue = Functional Assessment of Chronic Illness Therapy–Fatigue; GPORWE = Global Patient Outcomes and Real World Evidence; IBDQ = Inflammatory Bowel Disease Questionnaire; ITT = intent-to-treat; mBOCF = modified baseline observation carried forward; MMRM = mixed model for repeated measures; CCI [redacted]; PGRC = Patient’s Global Rating of Change; PGRS = Patient’s Global Rating of Severity; QIDS-SR16 = Quick Inventory of Depressive Symptomatology–Self Report (16 Items); SAP = statistical analysis plan; SF-36 = 36-Item Short Form Health Survey.

